IRB-approved letter from [name] stating that research staff will contact them about the study unless they respond via e-mail or phone to opt-out. 7-10 days after the e-mails and letters are sent, KSP will call patients who did not opt-out to tell them about the study. We have approval to contact these patients from the Medical Director of Vanderbilt Primary care, and the primary care physicians at the clinics we are recruiting from.

Once enrolled, any participants randomized to FAMS will be asked if they want to invite an adult family member to participate. They can elect to invite a family member by providing the person's name and mobile phone number. KSP will then contact the family member to describe the study and formally invite them to participate (see also FAMS Recruitment and Enrollment Script Family Members).

Those participants who complete a follow-up survey electronically or via mailed paper copy will receive their materials along with a cover letter that explains the study components. KSP will fill out the information needed. Because this is a long study with several components, this letter and figure help to reiterate key points of the study, and we hope, also contribute to better retention. KSP will use the appropriate form based on how the participant will be completing the survey (e.g., online, mailed paper survey) and which items are needed for the timepoint (e.g., A1c, survey, both), fill it out with the applicable information, and these letters will be included when sending the online or paper follow-up survey materials.

Identify the criteria for inclusion and exclusion and explain the procedures that will be used to determine eligibility. If psychiatric/psychological assessments will be conducted (e.g., depression or suicidal ideation screenings), state who will administer, his/her experience, and how risks will be managed.

Patient inclusion criteria includes adults aged 18 years and older (per participant report and confirmed by a trained RA following informed consent); individuals with a diagnosis of T2DM; patient at a participating health center (Faith Family Medical Clinic, The Clinic at Mercury Courts, Vine Hill Community Clinic, Priest Lake Family & Women's Health Center, Neighborhood Health Clinics, and VUMC; see Faith Family, [name], and UCHS Letters of Support); and current treatment with oral and/or injectable daily diabetes medication.

Patient exclusion criteria includes non-English speakers; individuals reporting they do not have a cell phone; individuals unwilling and/or not able to give informed consent; individuals whose most recent A1c value, within 12 months, is <6.8%; individuals with unintelligible speech, a severe hearing impairment, or visual impairment; individuals reporting that a caregiver administers their diabetes medication; individuals unable to pass cognitive screening for eligibility; and individuals who cannot receive, read, and respond to a text message after instruction from a trained RA.

Upon recruitment, KSP will ask participants questions to pre-screen for eligibility either via telephone or in-person. If an individual meets those criteria and is interested in participating, KSP then schedule a time to complete eligibility screening and, if eligible, proceed to enrollment. Eligibility screening includes: a brief cognitive screening measure and a series of text message exchanges to ensure the participant is able understand, send, and receive text messages (see REACH Eligibility and Consent).

Family member inclusion criteria includes adults aged 18 years and older (per participant report and confirmed by a trained RA following informed consent); someone identified by the participant as part of their family (biologically or legally, or a close friend or roommate who is involved in the patients' daily routine).

Family member exclusion criteria includes non-English speakers; individuals reporting they do not have a cell phone; individuals unwilling and/or unable to give informed consent; and individuals with unintelligible speech, a severe hearing impairment, or visual impairment.

We will use several items we will use as part of our retention efforts with participants over the course of the 15 month trial. These include a t-shirt, water bottle, magnet, and birthday card with the REACH logo, and a brief seasonal newsletter. KSP will offer the magnet and t-shirt or water bottle over the course of the study in person at an upcoming survey assessment. If the participant completes their surveys via e-mail or a mailed survey, KSP will mail the item with the study materials. Our team will mail the birthday card during the month of the participants' birthday which is signed by the team members. The newsletter will be mailed to participants or e-mailed for those with whom e-mail is the preferred contact method. The newsletters offer information about community events, updates from our team, and recipe ideas. We will also e-mail a brief seasonal newsletter to a liaison at our partnering clinics to share with staff. This newsletter will have updates from our team and study progress.

Describe how the selection of participants is equitable in relation to the research purpose and setting.

Given our study aims, this research does not require systematic procedures to ensure equitable selection. We will enroll adults with T2DM that are diverse with respect to age, gender, race, and ethnicity.

Please indicate whether you plan to enroll any of the populations indicated below:

- VU Medical Students/trainees
- Students
- Elderly/Aged - targeted
- Subordinates/Employees
- Females of childbearing potential
- Terminally ill participants
- Healthy Volunteers
- Other**
- Minorities

Please specify 'Other' populations:

Adults with T2DM and their adult family members

Please identify ALL applicable recruitment methods:

- N/A
- Flyers**
- Internet
- Letter**
- Departmental Research Boards,
- Mass E-mail Solicitation/Research Notifications Email Distribution List
- Newspaper
- Posters
- ResearchMatch (IRB 090207)
- Radio
- Telephone**
- Television
- Social Media
- Other**

Please describe other:

We will use Subject Locator to identify patients prior to upcoming appointments at Vanderbilt Primary Care clinics and send an opt-out letter or email. We may also contact patients via e-mail if indicated as a preferred method of contact on an interest card (see REACH Recruitment Email). We will send a recruitment e-mail (see Clinic Recruitment Letters) for those potential participants identified by one of our partnered clinics based on their EMR queries who have an e-mail contact listed in their EMR. Additionally, we will recruit patients through face-to-face communication in the waiting rooms of participating clinics, as well as at clinic or community events. Providers at participating clinics may also refer patients to the study, and patients can call the REACH Helpline to receive more information about participation (see REACH Recruitment Script).

Will the study provide compensation to research participants?

- Yes**
- No

Date of IRB Approval: 04/09/2018

Institutional Review Board

Please specify the method of compensation.

Money

Please include information describing the payment amount and schedule.

Over the course of 15 months, participants can receive up to \$210 for completing five assessments and A1c tests. Payment is broken down as follows:

Baseline: \$20 Total (\$10 survey; \$10 A1c)
3 months: \$35 Total (\$15 survey; \$20 A1c)
6 months: \$50 Total (\$20 survey; \$30 A1c)
12 months: \$65 Total (\$25 survey; \$40 A1c)
15 months: \$40 Total (\$20 survey; \$20 A1c)

If participants complete screening but are ineligible to participate, they will receive \$10 as compensation for their time.

Additionally, FAMS participants will receive \$10 for their participation in diabetes coaching--for a total of up to \$60 (Phone coaching is offered once per month for six months). Family member participants will receive up to \$50--\$25 for the initial assessment and \$25 for the follow-up assessment at 6 months.

Participants receive payment via mailed Comdata cards. KSP submit payment information to our departmental budgets administration and then the VUMC card office, and the cards are pre-loaded and mailed to the participant. We will use mailed checks as a back-up method for participants who prefer to continue to receive a mailed check instead of the Comdata card.

Are you requesting a waiver for the collection of Social Security numbers?

Yes

No

Do you agree to release study information to Vanderbilt-approved list services, web sites or publications?

NOTE: Vanderbilt has a variety of list services and publications, such as the Clinical Trials Website. Posting research protocol information on research-related websites and other listing services, allows potential participants to search and find studies related to their condition or interest.

Yes, this information may be released as described in the lay summary.

No, do not release information to research-related web sites and other listing services.

Does this study include a certificate of confidentiality or sensitive research information that must be hidden in the medical record?

Yes

No

Radiation Procedures and Radioactive Drugs

Does this study involve any radiation ionizing procedures for research?

[] Yes

No

Drugs, Devices, Biologics

Please check all that apply:

N/A

- Drug(s)/Biologic(s) or Placebo (inactive substance) Used for Research that HAVE an IND
- Drug(s)/Biologic(s) or Placebo (inactive substance) used for Research that DO NOT have an IND [only include drugs that are being used outside of package insert labeling for indication, route of administration, dose, dosing frequency, dosage form, and/or population in which the drug is being used (i.e. children)]
- IBC Review for Live, Recombinant, and/or Attenuated Microorganisms for Vaccination, Gene Transfer or Botox
- Device(s) Used for Research (devices may also include computer software, in vitro diagnostics, etc.)

PHI/Consent

Please indicate what you plan to do with regard to consent (check all that apply):

Consent
 Waiver of Consent
[] Consent was obtained in another study
[] Consenting not required (e.g., exempt project, non-human project)

Please describe the specific steps for obtaining informed consent and the procedures that will be utilized to protect the privacy of individuals.

Following recruitment, a member of the research team will schedule each patient for an enrollment appointment at the clinic where they receive care. During this time, a trained RA will go through the process of informed consent, reviewing the consent document verbally (see REACH ICD and REACH RCT Survey), allowing the patient to review the informed consent document, and then obtaining informed consent for participation in this research. The patient can ask questions at any point during the consent process. As part of the informed consent process, the RA will explain the procedures in place to protect the privacy and confidentiality of participants.

Patient participants randomly assigned to FAMS will have the option to invite a family member by providing that person's name and phone number. A trained RA will then call the family member to screen them for eligibility, tell this person more about the study, including the benefits and risks of participation, and ask if they are willing to participate (see FAMS Recruitment and Enrollment Script Family Members). Family members can also receive this information they agree to over the phone regarding their participation via mail or e-mail for their records (see FAMS Family Member Informed Consent).

Does the person obtaining consent have an existing relationship with the participant(s)?

[] Yes
 No

Please describe any waiting periods between informing potential participants of the research and obtaining consent, if applicable.

Some patients may learn about the study from their provider or by viewing a flyer in the clinic waiting room. Such participants can fill out an interest card and a trained RA will contact them to describe the study, screen for eligibility, and complete an enrollment survey. We anticipate the time between the completion of an interest card and RA contact to be less than one week. For some patients, there will be no waiting period because they learn of the study from an RA in the clinic waiting room and then, if interested and eligible, enrollment/baseline processes are completed on the same day.

Will surrogate consent be requested?

[] Yes
 No

How will non-English speaking participants be consented?

A translated written informed consent document in a language understandable to the participant. This should be an accurate translation of the full informed consent document (consider having a translator present during the consenting process should the participant have any questions).

Orally, using a qualified translator to translate the English informed consent document to the participant, and a translated short form in a language understandable to the participant. (See "Documentation of Informed Consent" at IRB Policy IV.B for details).

Enrolling only English speaking participants.

Please provide a justification for only enrolling English speaking participants.

At this time, the study content (delivered via SMS) is available only in English.

Which type of waiver is being selected (check all that apply):

Waiver of Documentation

Alteration of Informed Consent Process

Waiver of Informed Consent Process/Waiver of Authorization

The IRB may waive the requirement to obtain a signed informed consent document for some or all of the participants. This is a waiver of signatures only. With this option, all of the other basic elements of informed consent are still present and are provided to participants.

The only record linking the participant to the research is the consent document and the principal risk would be potential harm resulting from a breach of confidentiality. Under this condition, each participant must be asked whether he/she wants to sign a consent document. The IRB must review and approve the consent document.

The research is minimal risk and involves no procedures for which written consent is normally required outside of the research context (e.g. phone surveys, collection of de-identified data from medical record or other chart review). The IRB must review and approve the consent document or script.

Are you requesting a waiver of authorization to access (use) Protected Health Information (PHI)?

Yes

No

Please describe the plan to protect the identifiers from improper use and disclosure.

Participants will be assigned a unique subject ID associated with their identifiable information. Family member participants' information is linked to the patient participant. Original paper copies of informed consent documents and completed interest cards will be filed in a locked cabinet in the Center for Health Behavior and Health Education (CHBHE). All transcripts, surveys, text message response data, and audio-recordings will be de-identified. Survey data will be recorded and stored electronically (via REDCap), separate from identifiable information used to contact or follow-up with participants. All identifiable information used to contact or follow-up with participants will be stored without any health information, and is password protected and retained on a secure VUMC server until the close of the study, at which point it will be destroyed. Participants' responses to two-way text messages are never associated with identifiable information, but will be associated with participants' unique subject ID. Participant identifiers will be retained only for financial or regulatory research purposes, and are password-protected and stored separately from any associated data. Only trained KSP will have access to participant data.

Will Protected Health Information (PHI) be accessed (used) in the course of screening/recruiting for this research?

Yes
 No

Does this research use or disclose Protected Health Information (PHI)?

Yes
 No

Please indicate the source of the PHI to be collected.

Medical records and data previously collected for research purposes.

Please indicate when PHI will no longer be accessed.

Closure of the study

Please describe the plan to destroy the identifiers at the earliest opportunity consistent with the conduct of the research, unless there is a health or research justification for retaining the identifiers or such retention is otherwise required by law.

Participant identifiers will be retained only for financial or regulatory research purposes. All identifiable information used to contact or follow-up with participants will be stored without any health information, and will be password protected and retained on a secure VUMC server until the close of the study, at which point this information will be destroyed.

Conflict of Interest Disclosure

Is there a potential conflict of interest for the Principal Investigator or key personnel? • The PI is responsible for assuring that no arrangement has been entered into where the value of the ownership interests will be affected by the outcome of the research and no arrangement has been entered into where the amount of compensation will be affected by the outcome of the research. • Assessment should include anyone listed as Principal Investigator, or other research personnel on page 1 of this application. Please note that ownership described below apply to the aggregate ownership of an individual investigator, his/her spouse, domestic partner and dependent children). Do not consider the combined ownership of all investigators.

Yes

No

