This IRB application addresses the second of three aims for our overall research plan: to evaluate a mobile-phone delivered medication adherence intervention (called REACH; Rapid Education/Encouragement And Communications for Health) and test intervention effects on adherence and glycemic control among low income adults with type 2 diabetes mellitus (T2DM) receiving primary care at Federally Qualified Health Centers (FQHCs) or VUMC. In addition, family-focused components (called FAMS; Family-focused Add-on to Motivate Self-care) are integrated with the larger REACH intervention, and include diabetes coaching, goal-focused text messages delivered to the patient, and supplemental text messages delivered to an identified adult family member. We will evaluate the effects of the supplemental, family-focused intervention on family members' supportive and obstructive behaviors, patients' diabetes self-efficacy, and patients' adherence to diet and exercise. (Aim 1, to improve the content and functionality of an existing mobile phone-delivered medication adherence promotion intervention for consistency with the Information-Motivation-Behavioral skills model and clear health communication strategies, and test for usability and acceptability with patients, received approval [see IRB #140562] in April 2014.)

Expected duration of the study.

We expect to complete data collection by the end of 2019, but the study will remain open for analyses and manuscript writing/submissions for an additional five years.

The IRB needs to understand how this study adds to the knowledge on this topic in order to be able to judge the risks and benefits to the research participants.

BACKGROUND

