We hypothesize that our SMS intervention will effectively improve medication adherence and glycemic control. We base this on our prior work and that of others. For instance, a 2012 study reported that patients with HIV who used an SMS intervention for 6 months were more optimally adherent even after intervention discontinuation [74]. In addition, in an SMS intervention with adults with T2DM, 100% of participants said they would recommend the program to family/friends with diabetes [75] and many actually did so [76], but to date no study has explored adult patients' receptivity to engaging their family members in SMS interventions about their own health and/or the potential benefits of doing so [77-79]. This is an important first step in expanding the reach of mHealth interventions to family members, who are at-risk for T2DM [80-82]. Rather than trying to change family members' behaviors directly, the supplemental family-focused intervention will target patients' ability to identify family behaviors that support or impede their self-care goals and enhance skills to ask for needed support and manage obstructive behaviors.

REFERENCES

1. Cramer JA: A systematic review of adherence with medications for diabetes. *Diabetes Care* 2004, 27:1218-1224.

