We may use text messages to correspond with participants who are enrolled in the study. Typically, we use phone calls to communicate with participants about study information (e.g., remind them about upcoming study appointments, confirm receipt of a mailed survey). We will use text messages as a back-up method of communication in our attempts to reach participants about relevant study information.

For potential participants at Faith Family Medical Center, clinic pharmacists will also give patients a half-page insert when they pick up their diabetes medication at the clinic pharmacy. Additionally, we will recruit participants from our previous research studies who indicated they would like us to contact them for future research studies. These individuals will be contacted by their preferred method (e.g. cell phone), and invited to participate.

Patients can also contact research staff via the REACH Helpline if they are interested in participating after learning about REACH at their clinic (see REACH Recruitment Script).

VUMC patient recruitment: We will also locate potential participants meeting eligibility criteria at Vanderbilt locations through specific tools including subject locator, my research at vanderbilt (MRAV), and research derivative. Subject Locator will be used as a recruitment tool to identify potential research subjects based on available in VU clinical systems (e.g. STAR Panel, WizOrder, Clinic Scheduling). The Subject Locator program is part of a toolset available through VICTR that enables teams to specify inclusion/exclusion criteria for a specific study. The inclusion/exclusion criteria are codified for computable use and combined with data coming through VU Clinical Systems to proactively identify individuals who might qualify for a study. KSP will use Subject Locator to identify patients who met eligibility criteria. KSP will then conduct EHR review to confirm the patient met eligibility criteria. We then e-mail or mail all identified patients an

Date of IRB Approval: 04/09/2018

Institutional Review Board

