**REACH Intervention:
Improving Medication Adherence Among Underserved Patients With Type 2 Diabetes**

NCT02409329

03/31/2020

NCT02409329 – Statistical Analysis plan

REACH treatment effects – any REACH vs. Control

All analyses were performed using R v.3.5.1. We employed multiple imputation with chained equations to address missing data ($m=1,000$ imputed datasets). Statistical significance for each hypothesis test was determined at the $\alpha=0.05$ level. All analyses compare those receiving the REACH intervention (i.e., REACH or REACH + FAMS) to control except for the subgroup analyses estimating additional effects of also receiving FAMS.

We used generalized estimating equations (GEE) with a working-exchangeable correlation structure and identity link (1), adjusting for baseline and allowing a time-treatment interaction. We adjusted for the baseline value of the outcome of interest with restricted cubic splines (three knots) to allow for a nonlinear effect of the baseline value. For each outcome, we performed an omnibus test of the treatment effect using a robust variance-covariance based Wald statistic. We used ordinary least squares linear regression with Huber-White heteroscedasticity-consistent standard errors (2) to obtain point estimates and 95% CIs for the intervention effect on each outcome at each time point.

REACH only and REACH+FAMS vs. Control

Half of the intervention group received REACH only and the other half received REACH+FAMS for the first 6 months. Both intervention groups received REACH only during months 6-12. Data visualizations suggested effect modification by baseline HbA1c, in which those with a higher baseline HbA1c demonstrate a larger estimated effect at 3 and 6 months than those with a lower baseline HbA1c. To increase our power to detect any differential effects for REACH only as compared to REACH+FAMS, we conducted analyses with a subset of data including participants with a baseline HbA1c $\geq 8.5\%$ (69 mmol/mol; $n=219$), which was the approximate mean value for baseline HbA1c. With this reduced dataset, we conducted the same GEE model described above for REACH only vs. control and, separately for REACH+FAMS vs. control. We used ordinary least squares linear regression with Huber-White heteroscedasticity-consistent standard errors (2) to obtain point estimates and 95% CIs for the intervention effect on each outcome at each time point.

References:

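### Does recruiting from the team's earlier studies, with no stated check for prior exposure to REACH, require a change to the plan?

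*Protocol*

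**What the plan says.** The Recruitment section of the protocol lists several routes into the trial. One reads: "we will recruit participants from our previous research studies who indicated they would like us to contact them for future research studies". It does not say which studies are meant, and the only condition is earlier agreement to be contacted.

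The protocol's opening statement of purpose presents this trial as the second of three aims. It describes the preceding one as "Aim 1, to improve the content and functionality of an existing mobile phone-delivered medication adherence promotion intervention" and adds that the work was to "test for usability and acceptability with patients, received approval" in April 2014 under a separate IRB number. So at least one earlier study put a version of the intervention in front of patients.

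The eligibility text, also under Recruitment, opens its exclusions with "Patient exclusion criteria includes non-English speakers; individuals reporting they do not have a cell phone" and continues through A1c, impairments, caregiver-administered medication, cognitive screening and ability to text. Prior participation is not listed. The screening it describes is a cognitive measure and a text exchange. The eligibility and consent form it refers to is not among the documents.

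The SAP adjusts for the baseline value of each outcome. It states "All analyses compare those receiving the REACH intervention (i.e., REACH or REACH + FAMS) to control except for the subgroup analyses", and its one restricted analysis is by baseline HbA1c. It has no term, count or sensitivity analysis for prior exposure.

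**The concern.** Read together, these sections open a route by which someone who had already used a forerunner of REACH could be randomised, and they describe no step that would identify that person. Someone who has already absorbed part of the benefit may gain less from a second course. Among such people the contrast between REACH and control would be smaller than among newcomers, and the overall estimate would be pulled toward the null. The protocol's own rationale takes persistence of benefit seriously: it cites a study in which "patients with HIV who used an SMS intervention for 6 months were more optimally adherent even after intervention discontinuation".

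At stake would be some loss of effect size and power. A reader of a small or null result would also not know whether previously exposed participants had contributed to it.

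**Working it through.** **What the documents establish.** They show that the route exists and that no check is described. They do not show that Aim 1 participants were offered later contact, were invited, or enrolled. The protocol also describes earlier work by the team with no intervention mentioned: 314 patients in the Background section and 179 patients sampled in 2013 in the Significance section. Either could be the source of re-contacted people. The size of Aim 1 and the length of exposure in it are not given. The cited HIV study involved 6 months of use, so it says little about what usability testing leaves behind.

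**Direction.** Exposure would precede randomisation, so it is balanced between arms on average and cannot confound the comparison. A carry-over gain that is equal in all arms cancels, and the baseline adjustment largely absorbs it. What remains is a reduced response to REACH among the exposed.

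**Inputs.** The accrual goal of 525 comes from the Subject Population(s) section of the protocol, and alpha = 0.05 from the SAP (taken as two-sided). The rest is assumed, because the documents give no value:
- p, the share exposed: 1% to 10%, about 5 to 52 people
- f, the fraction of the effect already realised in them: 0.1 to 1
- power without exposure: 80%, a noncentrality of 0.8416 + 1.9600 = 2.8016

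**Formulas.**
- Observed effect = (1 − p·f) × true effect
- Power with everyone kept = Φ(2.8016 × (1 − p·f) − 1.96)
- Power with the exposed dropped and not replaced = Φ(2.8016 × √(1 − p) − 1.96)
- Expected shift in the estimate when they are dropped = 2.8016 × p·f, in standard errors of the full analysis
- Chance variation (SD) of that shift = √(1/(1 − p) − 1), in the same units

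| p | f | Attenuation | Power, all kept | Power, exposed dropped | Expected shift (SE) | Chance variation (SE) |
|---|---|---|---|---|---|---|
| 1% | 0.1 | 0.1% | 79.9% | 79.6% | 0.003 | 0.10 |
| 5% | 0.5 | 2.5% | 78.0% | 78.0% | 0.07 | 0.23 |
| 10% | 0.5 | 5% | 75.9% | 75.7% | 0.14 | 0.33 |
| 10% | 1 | 10% | 71.3% | 75.7% | 0.28 | 0.33 |

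For the second row: 1 − 0.05 × 0.5 = 0.975; 2.8016 × 0.975 − 1.96 = 0.772; Φ(0.772) = 78.0%. The shift is 2.8016 × 0.025 = 0.07, and the chance variation is √(1/0.95 − 1) = 0.23.

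**What each possible change would gain.**
- *Dropping exposed participants.* Power rises only if f exceeds (1 − √(1 − p))/p, which is 0.501, 0.506 and 0.513 for p = 1%, 5% and 10%. Below about one half, dropping them costs power.
- *A sensitivity model without them.* The ratio of expected shift to chance variation is 2.8016 × f × √(p(1 − p)). For p up to 10% and f = 1 it is at most 2.8016 × 0.3 = 0.84. The shift stays below one standard deviation of its own noise throughout the assumed range, so the result would not be interpretable either way.
- *An exclusion rule for further recruitment.* The protocol expected data collection to finish by the end of 2019. With a last assessment at 15 months, enrolment on that schedule would have ended around autumn 2018. The SAP is dated 03/31/2020, is written in the past tense and reports a realised subset (n = 219). There appears to be nobody left for such a rule to apply to.

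**The case for a change.** The strongest opposing case is that the gap is real and cheap to close. The team contacted these people itself, and the PHI/Consent section names its data sources as "Medical records and data previously collected for research purposes", so a record match looks feasible. The protocol keeps the study open for analysis and writing for five years after data collection. A count by arm takes one table row, and if it is zero one sentence settles the matter.

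Much of this stands. It would be useful for a report to state how many participants in each arm had received an earlier version of REACH. But that adds to the reporting and corrects nothing in the plan. It also shows that prior exposure is not beyond checking; a check is simply not planned. The unsupplied eligibility form may even contain one.

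It can also be said that p might exceed 10%. At p = 20% and f = 1 power would fall to 61.1%, and the shift on dropping the exposed (2.8016 × 0.20 = 0.56 SE) would slightly exceed its chance variation (√(1/0.8 − 1) = 0.50 SE). That case needs 105 of the 525 to be former users for whom usability testing had already delivered the whole effect. Nothing in the documents points that way. Nor do they show that prior exposure lowers response rather than raising it.

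**Conclusion.** No change to the plan. Recruiting people who agreed to further contact is a fair trade-off: it helps accrual, and the comparison of all randomised participants remains unconfounded. Any cost is a loss toward the null of about p·f. That is 2.5% of the effect and 2 power points at p = 5% and f = 0.5, and 10% of the effect at an unlikely extreme (p = 10%, f = 1). These figures rest on assumed values of p, f and 80% power, and on the unproven premise that exposed people enrolled at all. A sensitivity analysis would be swamped by its own noise over that range, and an exclusion rule appears to come after enrolment closed. The analysts can state the number exposed by arm from their own records if they wish.
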